5.4.11 Endocrine Disorders

Management of cabozantinib associated endocrine disorders:

Prospective studies of markers of thyroid functions are currently ongoing in two single-agent studies to characterize the effects of cabozantinib on thyroid function. Preliminary data indicate that cabozantinib affects thyroid function tests (TFTs) in a high number of subjects (see Cabozantinib Investigator's Brochure). Routine assessments for signs and symptoms associated with thyroid dysfunction is recommended for subjects treated with cabozantinib.

Management of thyroid dysfunction (e.g., symptomatic hypothyroidism) should follow accepted clinical practice guidelines.

Other endocrine disorders such as hypocalcemia and hyperglycemia, and associated laboratory changes, have been observed in less than 10% of subjects. Monitoring with standard laboratory tests and clinical examination prior to initiation and during treatment with cabozantinib is required.

[figure not shown]
Cabozantinib should be discontinued in subjects with severe or life-threatening endocrine dysfunction.

Immune-related endocrine disorders

Endocrine Hypophysitis Adrenal Insufficiency	Management/Next Dose for Nivolumab+/-Ipilimumab
≤ Grade 1	Asymptomatic TSH elevation * Consider thyroid replacement therapy and endocrine consult
Grade 2	Hold until patients are on a stable replacement hormone regimen. If treated with steroids patients must be stable off steroids for two weeks. Resume at same dose level.
Grade 3	Off study treatment.
Grade 4	Off protocol therapy
Note all patients with symptomatic pituitary enlargement, exclusive of hormone deficiency, but including severe headache or enlarged pituitary on MRI should be considered grade 3 events. Isolated thyroid or testosterone deficiency may be treated as grade 2 if there are no other associated deficiencies and adrenal function is monitored.	
Prior to starting corticosteroids or hormone replacement for any reason, appropriate endocrine testing including cortisol, ACTH, TSH and T4 must be obtained to document baseline.	
* Note patients with thyroiditis may be retreated on replacement therapy. Patients must be evaluated to rule out pituitary disease prior to initiating thyroid replacement.	
- Patients with grade 3 thyroiditis and skin rash may continue therapy as for grade 2 events with resolution and stable replacement treatment.	
- Patients with thyroiditis or hypopituitarism who are stable as above may be restarted with replacement hormones including thyroid hormone and physiologic doses of corticosteroids.	
- Please note that grading and for hypophysitis with symptoms of headache, visual or neurologic changes or radiologic evidence of pituitary enlargement and other CNS events such as aseptic meningitis or encephalitis should be considered grade 3 events.	
Recommended management: See Endocrine Management Algorithm	

Endocrinopathy Management Algorithm

Rule out non-inflammatory causes. If non-inflammatory cause, treat accordingly and continue immuno-oncology (I-O) therapy.
Consider visual field testing, endocrinology consultation, and imaging.

Patients on IV steroids may be switched to an equivalent dose of oral corticosteroids (e.g. prednisone) at start of tapering or earlier, once sustained clinical improvement is observed. Lower bioavailability of oral corticosteroids should be taken into account when switching to the equivalent dose of oral corticosteroids.

5.4.12 Neurologic Events

Management of cabozantinib associated neurologic events:

[figure not shown]
Neurologic events are unusual with cabozantinib. Reversible leukoencephalopathy syndrome (RPLS) can be considered, but generally immune related events should be excluded as well. If a diagnosis of RPLS is confirmed, cabozantinib should be permanently discontinued.

Immune-related neurologic events

Neurologic events	Management/Next Dose for Nivolumab
≤ Grade 1	Hold dose pending evaluation and observation. Resume with no change in dose when resolved to baseline.
Grade 2	Hold dose pending evaluation and observation. Hold until ≤ Grade 1. Off protocol therapy if treatment with steroids is required. Resume at same dose level for peripheral isolated n. VII (Bell's palsy) [^]
Grade 3	Off protocol therapy
Grade 4	Off protocol therapy
Patients with any CNS events including aseptic meningitis, encephalitis, symptomatic hypophysitis, or myopathy, peripheral demyelinating neuropathy, cranial neuropathy (other than peripheral n. VII), GB syndrome, myasthenia gravis should be off study.	
Recommended management: See Neurologic Adverse Event Management Algorithm	

Neurological Adverse Event Management Algorithm

Rule out non-inflammatory causes. If non-inflammatory cause, treat accordingly and continue I-O therapy.

Patients on IV steroids may be switched to an equivalent dose of oral corticosteroids (e.g. prednisone) at start of tapering or earlier, once sustained clinical improvement is observed. Lower bioavailability of oral corticosteroids should be taken into account when switching to the equivalent dose of oral corticosteroids.

5.4.13 Renal dysfunction and proteinuria

Management of cabozantinib related proteinuria: Proteinuria has been reported with approved drugs that inhibit VEGF pathways as well as with cabozantinib. Any level of proteinuria diagnosed by dipstick should be quantified by a UPCR (mg/dL protein / mg/dL creatinine). When a UPCR exceeds 1, a repeat UPCR or a 24-hour urine protein and creatinine should be performed to confirm the result. Cabozantinib should be discontinued in subjects who develop nephrotic syndrome (proteinuria > 3.5 g/day in combination with hypoalbuminemia, edema and hyperlipidemia) or any other relevant renal disease. Also, given the nephrotoxic potential of bisphosphonates, these agents should be used with caution in patients receiving treatment with cabozantinib. Details of management are described in the next Table below

Severity of Proteinuria (UPCR)	Management of Proteinuria
≤ 1 mg/mg (≤ 113.1mg/mmol)	
 No change in cabozantinib treatment or monitoring
> 1 and < 3.5mg/mg (> 113.1 and < 395.9mg/mmol)	
 Consider confirming with a 24-h protein assessment within 7 days No change in cabozantinib treatment required if UPCR ≤ 2 mg/mg or urine protein ≤ 2 g/24 h on 24-h urine collection. Dose reduce or interrupt cabozantinib treatment if UPCR > 2 mg/mg on repeat UPCR testing or urine protein > 2 g/24 h on 24-h urine collection. Continue cabozantinib on a reduced dose if UPCR decreases to < 2 mg/mg. Consider interrupting cabozantinib treatment if UPCR remains > 2 mg/mg despite a dose reduction until UPCR decreases to < 2 mg/mg. Restart cabozantinib treatment at a reduced dose after a dose interruption. Repeat UPCR within 7 days and once per week. If UPCR < 1 mg/mg on 2 consecutive readings, UPCR monitoring can revert to protocol-specific times. (Second reading is confirmatory and can be done within 1 week of first reading.) If UPCR remains > 1 mg/mg and < 2 mg/mg for 1 month or is determined to be stable (< 20% change) for 1 month, check urine protein/creatinine per protocol or as clinically indicated.
≥ 3.5mg/mg (≥ 395.9mg/mmol)	
 Interrupt cabozantinib treatment pending repeat UPCR within 7 days and/or 24-h urine protein. If ≥ 3.5 mg/mg on repeat UPCR, continue to interrupt cabozantinib treatment and check UPCR every 7 days. If UPCR decreases to < 2 mg/mg, restart cabozantinib treatment at a reduced dose and monitoring of urine protein/creatinine should continue weekly until the UPCR decreases to < 1 mg/mg. If UPCR remains > 1 mg/mg and < 2 mg/mg for 1 month or is determined to be stable (< 20% change) for 1 month, check urine protein/creatinine per protocol or as clinically indicated.
Nephrotic syndrome	
 Discontinue cabozantinib treatment

RCC, renal cell carcinoma; UC, urothelial carcinoma; UPCR, urine protein/creatinine ratio.

[figure not shown]
Immune-related renal dysfunction

Renal	Management/Next Dose for Nivolumab and Nivo/Ipi combination
≤ Grade 1	Continue study therapy
Grade 2	Hold until ≤ Grade 1. Resume at same dose level.
Grade 3	Hold until ≤ Grade 1. Resume at same dose level.
Grade 4	Off treatment

Patients with fever should be evaluated as clinically appropriate. Patients may experience isolated fever during infusion reactions or up to several days after infusion. Evaluation over the course of 1-2 weeks should be done for other autoimmune events that may present as fever

Renal Adverse Event Management Algorithm

Rule out non-inflammatory causes. If non-inflammatory cause, treat accordingly and continue I-O therapy

Patients on IV steroids may be switched to an equivalent dose of oral corticosteroids (e.g. prednisone) at start of tapering or earlier, once sustained clinical improvement is observed. Lower bioavailability of oral corticosteroids should be taken into account when switching to the equivalent dose of oral corticosteroids.

Rev. Add4

5.4.14 Fatigue

Management of cabozantinib associated fatigue: Fatigue is common with cabozantinib treatment and generally should resolve within 2 weeks of discontinuing therapy. Dose reduction can be considered.

Immune-related fatigue

Fatigue	Management/Next Dose for Nivolumab+/-Ipilimumab
≤ Grade 1	No change in dose.
Grade 2	No change in dose

Fatigue	Management/Next Dose for Nivolumab+/-Ipilimumab
Grade 3	Hold until \leq Grade 2. Resume at same dose level.
Fatigue is the most common adverse event associated with immune checkpoint therapy. Grade 2 or greater fatigue should be evaluated for associated or underlying organ involvement including pituitary, thyroid, and hepatic, or muscle (CPK) inflammation.	

5.4.15 Fever

Management of cabozantinib associated fever. Fever is unusual with cabozantinib treatment. Infection and immune related etiologies should be considered.

Immune related fever

Fever	Management/Next Dose for Nivolumab and Nivo/Ipi combination
\leq Grade 1	Evaluate and continue at same dose level
Grade 2	Hold until \leq Grade 1. Resume at same dose level.
Grade 3	Hold until \leq Grade 1. Resume at same dose level.
Grade 4	Off treatment
Patients with fever should be evaluated as clinically appropriate. Patients may experience isolated fever during infusion reactions or up to several days after infusion. Evaluation over the course of 1-2 weeks should be done for other autoimmune events that may present as fever	

Rev. Add1
Rev. Add3

5.4.16 Infusion reactions

Since nivolumab contains only human immunoglobulin protein sequences, it is unlikely to be immunogenic and induce infusion or hypersensitivity reactions. However, if such a reaction were to occur, it might manifest with fever, chills, rigors, headache, rash, urticaria, angioedema, pruritis, arthralgias, hypo- or hypertension, bronchospasm, or other symptoms.

All Grade 3 or 4 infusion reactions should be reported as an SAE according to Section 5.2.9 if reporting criteria are met. Infusion reactions should be graded according to NCI CTCAE guidelines.

Treatment recommendations are provided below and may be modified based on local treatment standards and guidelines as medically appropriate:

Remain at bedside and monitor subject until recovery from symptoms

For Grade 1 symptoms: (Mild reaction; infusion interruption not indicated; intervention not indicated)

Infusion rate may be slowed or interrupted and restarted at 50% of the original infusion rate when symptoms resolve; if no further complications ensue after 30 minutes, the rate may be increased to 100% of the original infusion rate. Monitor patient closely.

The following prophylactic premedications are recommended for future infusions: diphenhydramine 50 mg (or equivalent) and/or paracetamol 325 to 1000 mg (acetaminophen) at least 30 minutes

before additional nivolumab administrations, slowing infusion rate as above.

For Grade 2 symptoms: (Moderate reaction requires therapy or infusion interruption but responds promptly to symptomatic treatment [e.g., antihistamines, non-steroidal anti-inflammatory drugs, narcotics, corticosteroids, bronchodilators, IV fluids]; close observation for recurrence and treatment medications may need to be continued for 24-48 hours), and no further nivolumab will be administered at that visit.

Stop the nivolumab infusion, begin an IV infusion of normal saline, and treat the subject with diphenhydramine 50 mg IV (or equivalent) and/or paracetamol 325 to 1000 mg (acetaminophen); remain at bedside and monitor patient until resolution of symptoms.

Corticosteroid or bronchodilator therapy may also be administered as appropriate. If the infusion is interrupted, then restart the infusion at 50% of the original infusion rate when symptoms resolve; if no further complications ensue after 30 minutes, the rate may be increased to 100% of the original infusion rate. Monitor patient closely. If symptoms recur, re administer diphenhydramine 50 mg IV, and remain at bedside and monitor the patient until resolution of symptoms. The amount of study drug infused must be recorded on the electronic case report form (eCRF).

The following prophylactic premedications are recommended for future infusions: diphenhydramine 50 mg (or equivalent) and (acetaminophen) (or paracetamol) 325 to 1000 mg should be administered at least 30 minutes before additional nivolumab administrations. If necessary, corticosteroids (recommended dose: up to 25 mg of IV hydrocortisone or equivalent) may be used.

For Grade 3 or Grade 4 symptoms: (Severe reaction),

Grade 3 symptoms: prolonged [i.e., not rapidly responsive to symptomatic medication and/or brief interruption of infusion]; recurrence of symptoms following initial improvement; hospitalization indicated for other clinical sequelae [e.g., renal impairment, pulmonary infiltrates]).

Grade 4 symptoms: (life threatening; pressor or ventilatory support indicated)

Nivolumab will be permanently discontinued

Immediately discontinue infusion of nivolumab. Begin an IV infusion of normal saline, and bronchodilators, epinephrine 0.2 to 1 mg of a 1:1,000 solution for subcutaneous administration or 0.1 to 0.25 mg of a 1:10,000 solution injected slowly for IV administration, and/or diphenhydramine 50 mg IV with methylprednisolone 100 mg IV (or equivalent), as needed. Patient should be monitored until the investigator is comfortable that the symptoms will not recur.

Investigators should follow their institutional guidelines for the treatment of anaphylaxis. Remain at bedside and monitor patient until recovery from symptoms.

In the case of late-occurring hypersensitivity symptoms (e.g., appearance of a localized or generalized pruritis within 1 week after treatment), symptomatic treatment may be given (e.g., oral antihistamine, or corticosteroids). Additional treatment prior to next dose as per guidelines above.

Please note that late occurring events including isolated fever and fatigue may represent the presentation of systemic inflammation. Please evaluate accordingly.

5.4.17 Embolism and Thrombosis

Management of cabozantinib associated embolism and thrombosis: Deep vein thrombosis and PE have been observed in clinical studies with cabozantinib; including fatal events (please refer to the Investigator Brochure). Subjects who develop a PE or DVT should have all study treatment held until therapeutic anticoagulation is initiated.

Anticoagulation with warfarin is not allowed due to drug interactions with both cabozantinib; therefore ONLY heparins or low molecular weight heparin is allowed. Patients with brain metastases should be treated with caution and the investigator should consider the potential benefit to outweigh the risks.

Grade 2-3 DVT or PE: All study treatment may be resumed without a dose-level reduction in subjects who have uncomplicated PE or DCT. During treatment with anticoagulants, subjects need to be monitored on an ongoing basis for bleeding risk and signs of bleeding.

Grade 4 DVT or PE: Subjects with life-threatening PE or DVT should have cabozantinib discontinued unless toxicity can be managed and subject is deriving clear clinical benefit as determined by the investigator and agreed by the Study Chair. Venous filters (e.g. vena cava filters) are not recommended due to the high incidence of complications associated with their use. Once a subject is fully anticoagulated, cabozantinib can be restarted per investigator judgment at one dose lower. Subjects should permanently discontinue cabozantinib after a second thrombotic event. Although routine prophylactic anticoagulation is not necessary for all subjects, prophylactic anticoagulation is allowed for individual subjects at the discretion of the investigator.

Arterial thrombotic events (e.g., transient ischemic attack, myocardial infarction) have been observed rarely in studies with cabozantinib. Cabozantinib should be discontinued in subjects who develop an acute MI or any other clinically significant arterial thromboembolic complication.

5.4.18 Hypertension

Management of cabozantinib related hypertension: Hypertension is a relatively common complication of other VEGF-pathway inhibitors and has been observed in cabozantinib clinical studies.

Guidelines for management are presented in the table below.

Table: Management of Hypertension Related to Cabozantinib

Criteria for Dose Modifications	Treatment/Cabozantinib Dose Modification
Subjects NOT receiving optimized anti-hypertensive therapy	
> 150 mm Hg (systolic) ^a and < 160 mm Hg OR > 100 mm Hg (diastolic) and < 110 mm Hg	
 Optimize antihypertensive medications by adding new or additional antihypertensive medications and/or increase dose of existing medications. Reduce cabozantinib treatment by one dose level if optimal antihypertensive therapy (usually to include 3 agents) does not result in BP < 150 mm Hg systolic or < 100 mm Hg diastolic If subject is symptomatic interrupt cabozantinib treatment
≥ 160 mm Hg (systolic) OR ≥ 110 mm Hg (diastolic)	
 Reduce cabozantinib by one dose level or interrupt cabozantinib treatment per investigator discretion Add new or additional anti-hypertensive medications and/or increase dose of existing medications and monitor subject closely for hypotension. If optimized antihypertensive therapy (usually to include 3 agents) does not result in BP < 150 mm Hg systolic or < 100 mm Hg diastolic, cabozantinib treatment should be dose reduced further or interrupted Cabozantinib treatment should be dose interrupted if upper limits of systolic BP (≥ 160 mm Hg) are sustained and not adequately manageable or if systolic BP is > 180 mm Hg or diastolic BP > 110 mm Hg, or if subject is symptomatic Re-start cabozantinib treatment at the most tolerable dose and re-escalate only if BP falls to and is sustained at < 150 mm Hg systolic and < 100 mm Hg diastolic
Hypertensive emergency ^b	
 Discontinue cabozantinib treatment

BP, blood pressure.

^a The investigator may decide to initiate or adjust antihypertensive treatment at a lower threshold than systolic BP > 150 or diastolic BP > 100 based on their clinical judgment and assessment of the individual subject.

^b Hypertensive emergency is defined as uncontrolled elevated BP with clinical evidence of progressive or impending end-organ damage (eg, myocardial infarction/ischemia, intracranial hemorrhage, cerebral ischemia, pulmonary edema, encephalopathy, kidney damage).

5.4.19 Myocarditis

Management of cabozantinib related

cardiomyopathy/myocarditis: Cardiomyopathy has been reported with VEGF-pathway inhibitors, but myocarditis is very infrequent at most. Therefore, immune related causes should be primarily suspected but cabozantinib should also be held while workup is ongoing.

Management of immune related cardiomyopathy/myocarditis: Myocarditis, that may result in cardiomyopathy, has been increasingly reported as a complication of immunotherapy.

Guidelines for management are presented in the table below.

- Drug will be held for grade 2 cardiac dysfunction pending evaluation
- Drug will be permanently discontinued for grade 3 or 4 cardiac dysfunction and grade 2 events that do not recover to baseline or that reoccur
- Treatment with steroids as clinically indicated

Cardiac*	Management/Next Dose for BMS-936558 (Nivolumab) + Ipilimumab Cardiac Toxicities
≤ Grade 1	Hold dose pending evaluation and observation** Evaluate for signs and symptoms of CHF, ischemia, arrhythmia or myositis. Obtain history EKG, CK (for concomitant myositis), CK-MB, Troponin I. Repeat troponin, CK and EKG 2-3 days. If troponin and labs normalize may resume therapy. If labs worsen or symptoms develop then treat as below. Hold pending evaluation.
Grade ≥ 2 with suspected myocarditis	Hold dose** Admit to hospital. Cardiology consult. Rule out MI and other causes of cardiac disease. Cardiac Monitoring. Cardiac Echo. Consider cardiac MRI and cardiac biopsy. Initiate high dose methylprednisolone. If no improvement within 24 hours, add either infliximab, ATG or tacrolimus. Consult algorithm for more details. Resume therapy if there is a return to baseline and myocarditis is excluded or considered unlikely.
Grade ≥ 2 with confirmed myocarditis	Off protocol therapy. Admit to CCU (consider transfer to nearest Cardiac Transplant Unit). Treat as above. Consider high dose methylprednisolone. Add ATG or tacrolimus if no improvement. Off treatment.

* Including CHF, LV systolic dysfunction, Myocarditis, CPK, and troponin
** Patients with evidence of myositis without myocarditis may be treated according as "other event"
NOTE: The optimal treatment regimen for immune mediated myocarditis has not been established. Since this toxicity has caused patient deaths, an aggressive approach is recommended.

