5.4.3 General principles for management of toxicity with combination therapy

The combinations of cabozantinib and immunotherapy are still investigational, and unanticipated or synergistic side effects may be observed. Toxicity from combination therapy may be difficult to attribute to cabozantinib versus nivolumab (with or without ipilimumab). Guidance is provided below in defining attribution by holding cabozantinib, or by empirically starting corticosteroids.

As a general approach, it is suggested that AEs be treated with supportive care when possible at the earliest signs of toxicity. The below management guidelines are provided based on what is known individually about cabozantinib and nivolumab/ipilimumab, with additional guidance in the areas of overlap. They are not mandatory and investigator discretion may be used.

There are many circumstances in which the instructions below dictate permanent discontinuation of therapy. If an investigator feels that it is in the patient's best interest to continue on study therapy, study chair approval may be obtained prior to restarting drug.

Table of relative likelihood of cabozantinib-related and immune-related toxicities.

++ More common

+ Less common

- Infrequent

Toxicity	Cabozantinib-related	Immune-related	Protocol management section
Diarrhea	++	++	5.4.6
Nausea and Vomiting	++	+	5.4.7
Oral mucositis	++	-	5.4.8
Hand-foot syndrome (palmar-plantar erythrodysesthesia syndrome)	++	-	5.4.8
Skin Rash	+	+	5.4.8
Transaminitis (AST/ALT increased)	+	++	5.4.9
Hyperbilirubinemia (bilirubin increased)	-	+	5.4.9
Amylase/lipase increased; pancreatitis	+	-	5.4.9
Pneumonitis	+	++	5.4.10
Hypothyroidism	++	++	5.4.11
Adrenal insufficiency	-	+	5.4.11
Neurologic events	-	+	5.4.12
Renal dysfunction	-	-	5.4.13
Proteinuria	+	-	5.4.13
Fatigue	++	++	5.4.14
Fever	-	-	5.4.15
Infusion reaction	N/A	-	5.4.16
Thrombosis/embolism	+	-	5.4.17
Hypertension	++	-	5.4.18
Cardiomyopathy/myocarditis	-	+	5.4.19
Hemorrhagic events	+	-	5.4.20
Fistula formation/perforation	+	-	5.4.21
Wound healing problems	+	-	5.4.22
Osteonecrosis of the jaw	+	-	5.4.23
Cardiac QTc prolongation	+	-	5.4.24

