5.4.7 Nausea and Vomiting

Management of cabozantinib-associated nausea and vomiting:

Antiemetic agents are recommended as clinically appropriate for treatment or prophylaxis of nausea and vomiting, along with supportive care. Dehydration and electrolyte abnormalities may be associated with vomiting and monitoring for and correction of fluid and electrolyte disturbances should be implemented. The dose modification guidance should be followed for non-hematologic events (Section [5.4.25](#)).

The 5-HT3 receptor antagonists are recommended over chronic use of NK-1 receptor antagonists and dexamethasone (NK-1 receptor antagonists can induce or inhibit CYP3A4, and glucocorticoids induce CYP3A4 and thus could lower cabozantinib exposure.)

Immune-related nausea and vomiting

Other GI N-V	Management/Next Dose for Nivolumab+/-Ipilimumab
≤ Grade 1	No change in dose.
Grade 2	Hold pending evaluation for gastritis duodenitis and other immune adverse events or other causes. Resume at same dose level after resolution to ≤ Grade 1.
Grade 3	Hold pending evaluation until ≤ Grade 1. Resume at same dose level. If symptoms do not resolve within 7 days with symptomatic treatment patients should go off protocol therapy
Grade 4	Off protocol therapy
Patients with grade 2 or 3 N-V should be evaluated for upper GI inflammation and other immune related events.	

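### Section 5.4.19 gives two different instructions for a recovered grade 3-4 cardiac event in which myocarditis is thought unlikely but has not been excluded

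*Combined protocol and SAP*

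**What the plan says.** Section 5.4.19, under its immune-related heading, has bullets followed by a table.

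- **Bullets.** Drug is held for grade 2 cardiac dysfunction while it is evaluated. Then: "Drug will be permanently discontinued for grade 3 or 4 cardiac dysfunction". The same bullet also stops drug for "grade 2 events that do not recover to baseline or that reoccur".
- **Table, suspected-myocarditis row (grade 2 and above).** Hold, admit, obtain a cardiology consult, work up and start high-dose steroid, with further immunosuppression if there is no improvement within 24 hours. The row refers the reader to an algorithm and ends: "Resume therapy if there is a return to baseline and myocarditis is excluded or considered unlikely".
- **Table, confirmed-myocarditis row (grade 2 and above).** Off protocol therapy.
- **Footnote on what counts as cardiac.** "Including CHF, LV systolic dysfunction, Myocarditis, CPK, and troponin".
- **Table header.** "Management/Next Dose for BMS-936558 (Nivolumab) + Ipilimumab Cardiac Toxicities". Other tables, such as the one in 5.4.7, are headed "Management/Next Dose for Nivolumab+/-Ipilimumab".
- **Note on the toxicity.** "Since this toxicity has caused patient deaths, an aggressive approach is recommended".

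Two general sections bear on this. Section 5.4.3 says of the management guidelines: "They are not mandatory and investigator discretion may be used". It adds that, where an instruction calls for permanent discontinuation, study chair approval may be obtained before restarting. Section 5.4.5 takes patients who need immunosuppression beyond steroids off immune therapy. It also lets a patient found not to need steroids for an autoimmune event resume at the investigator's discretion.

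**The concern.** A site with a recovered grade 3 or 4 cardiac event can find both a stop instruction and a resume instruction in the same section. Which one it follows settles whether immunotherapy is given again, and whether the question of study chair approval arises at all. The toxicity is one that the section itself describes as having been fatal.

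The row is also out of pattern. The other visible nivolumab/ipilimumab tables in 5.4 treat grades 2 and 3 on separate lines. Where they list grade 4, they take the patient off treatment, except for amylase/lipase elevation in 5.4.9. Elsewhere in 5.4 the study chair is named before restart after several serious events: grade 4 diarrhea (5.4.6), grade 4 transaminase elevation (5.4.9), grade 4 DVT or PE (5.4.17) and QTc prolongation (5.4.24).

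**Working it through.** There is no figure in the plan to reproduce. The check applies both texts to each kind of event.

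| Event | Bullets | Table and 5.4.5 | Result |
|---|---|---|---|
| Grade 2, first event, recovered, myocarditis excluded or unlikely | Held; no stop | Resume | Agree |
| Any grade ≥ 2, not back to baseline | Stop | Resume condition not met | Compatible |
| Grade 3-4, myocarditis confirmed | Stop | Off protocol therapy | Agree |
| Grade 3-4, needed immunosuppression beyond steroids | Stop | Off immune therapy under 5.4.5 | Agree |
| Grade 3-4, recovered, myocarditis excluded | Stop if read literally; arguably outside the immune-related heading | Resume | Conflict only on the literal reading |
| Grade 3-4, recovered on steroids at most, myocarditis unlikely but not excluded | Stop | Resume | **Conflict** |

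Three readings were tested.

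1. *Does the recovery condition in the bullet reach grades 3-4?* It follows the words about grade 2 events, and grade 2 has its own hold bullet. Extending it upward is the less natural reading.
2. *Do the two texts concern different events?* No. The footnote brings heart failure and LV systolic dysfunction into the table, so it overlaps the bullets' cardiac dysfunction, and the row's grade range includes 3 and 4.
3. *Does the immune-related heading remove the conflict?* It does so for cases where myocarditis is excluded. A case judged only unlikely has not been excluded, so both texts still apply. The row asks sites only to consider cardiac MRI and biopsy, so that judgement can be reached without either.

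A recurrent grade 2 event is stopped by the bullet, while the row does not mention recurrence. The point does not rest on this, but it is why the fix is worded for a first event.

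**Reach of the text.** Inputs are from 9.4 (144 randomized, up to 25 in Arm T) and 9.7 (1:1:1).

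- Header read literally (nivolumab plus ipilimumab): Arm C only, 144 / 3 = 48 planned patients; 48 / 169 = 28.4%.
- Header read as with or without ipilimumab: 144 + 25 = 169, since all four arms receive nivolumab (5.1).

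The broad reading is plausible: 5.3.2 lists myocarditis as a nivolumab risk, and 7.1 asks for ECG monitoring for myocarditis on all arms. Neither figure estimates events.

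**The case against.** The case for leaving the text alone has real force.

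- **The table may be meant to govern.** A sentence just before the bullets says that the management guidelines are in the table. That points to the table, but the bullets follow directly and are worded as firm instructions. It is not a ranking rule. The discretion to resume in 5.4.5 fits the row, but it has no grade limit and does not rank the two texts either.
- **The bullets are about immune-related events.** This stands, and it removes most of the argument for cases in which myocarditis is excluded.
- **The study chair route is permissive.** This also stands. A reader might infer that the row bypasses a mandatory approval. The documents do not support that: 5.4.3 says the guidelines are not mandatory and that approval may be obtained. What can be said is that the route attaches to a discontinuation instruction, so the bullet leads to it and the row does not.
- **The algorithm is not visible.** It may hold a grade rule that settles the matter, and text lost in PDF reading is not a defect of the plan.
- **There are backstops.** Confirmed myocarditis ends protocol therapy. The row requires admission and a cardiology consult. Section 5.4.26 stops treatment where the investigator sees substantial clinical risk. Serious grade 3-4 events with a hospital stay of at least 24 hours go to CTEP-AERS within 24 hours under 5.2.9, though that is notification and not approval.

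A reader might also infer that every recovered grade 3-4 cardiac event is affected, or that 48 or 169 patients are at risk. Neither follows: the first ignores the heading and 5.4.5, and the second confuses coverage of the text with occurrence of the event.

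**Conclusion.** The point holds in narrow form. For a grade 3-4 cardiac event with suspected myocarditis that returns to baseline without second-line immunosuppression, and in which myocarditis is considered unlikely but not excluded, the bullet stops drug and the row resumes it. No visible text says which applies.

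The group should be small, but the documents give no rate from which to size it. It is confined to Arm C if the header is taken literally. The responses to CTEP comments at the front of the document record that the study was suspended for slow accrual, so actual numbers may be below plan.

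The conclusion assumes that the recovery condition in the bullet belongs to grade 2 only, and that the unseen algorithm holds no grade rule that reconciles the two texts. The primary PFS analysis is unaffected. Severity: minor safety-text correction.

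**What to change.** Make the two texts agree.

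- **Row, last sentence.** Split it by grade. For a first grade 2 event, keep the present resume rule. For grade 3-4, discontinue as in the bullet unless myocarditis is excluded and another cause is established. If myocarditis is only considered unlikely, restart only after study chair approval under 5.4.3.
- **Bullet.** Add the matching exception to the grade 3-4 stop: unless myocarditis is excluded.

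This leaves immunotherapy available after an event shown not to be myocarditis and to have another cause. Study chair approval becomes a requirement only for the group in conflict, through a route the protocol already has. That is firmer than the permissive wording of 5.4.3, so the study chair and CTEP should confirm it. If the cited algorithm already contains a grade rule, the new wording should match it.

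The cost is one replaced sentence and one added clause, with no new procedures, patients or analyses.
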